2.1 Study Rationale

A First-in-Human (FiH) study with HMI-115 has already established the safety and tolerability of HMI-115 when administered subcutaneously in post-menopausal women aged between 45 to 65 years in single doses up to 240 mg and multiple doses up to 90 mg once every 2 weeks (Q2W) for 6 weeks¹. This study aims to evaluate the safety and efficacy of HMI-115 versus a placebo in pre-menopausal women aged 18 to 49 years diagnosed with moderate to severe endometriosis associated pain. The study will determine the safety and efficacy of HMI-115 at 60 mg Q2W, 120 mg Q2W, and 240 mg Q2W. Administration of different doses of HMI-115 together with placebo will allow for further evaluation of efficacy and safety of the drug and determine appropriate dose for future pivotal studies.

As a prove-of-concept study, change in dysmenorrhea (DYS) is used as the primary endpoint to show the preliminary efficacy of HMI-115 in endometriosis associated pain. Non-menstrual pelvic pain (NMPP) is considered as critical endometriosis associated pain, and is used for recruiting subjects with Composite Pelvic Signs and Symptoms Score (CPSSS) at least 2 for NMPP and evaluating NMPP by NRS as a secondary endpoint. Co-primary endpoints include DYS and NMPP would be used in the confirmative studies in future. In addition, a central laboratory will be used in this study for blood tests (including hormones). Dual energy X-ray absorptiometry (DXA) scan, as a bone mineral density (BMD) monitoring indicator, will be performed with a central reading. Transvaginal ultrasound (TVU), mainly to confirm the eligibility for study entry and to assess the condition of pelvis after administration of HMI-115, are suggested to be performed by the same staff from each site. Sellar MRI with contrast will also be performed locally for excluding subjects with pituitary tumor growth.

This study will not recruit subjects with obvious pre-existing mood disorders such as depression, bipolar disorder, besides, HMI-115 has not shown any potential of affecting subjects' mental state based on the mechanism of action, therefore, the mood state assessment by tools will not be involved at the current stage. However, if any sign of mental influence of HMI-115 is detected, a validated tool such as the Columbia-Suicide Severity Rating Scale will be used in the future studies.

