9.1 Statistical Hypotheses

The primary objective of the study is to evaluate the efficacy of HMI-115 for 12 weeks compared with placebo in the management of endometriosis-associated pain. This objective will be addressed by comparing the primary efficacy endpoint between each HMI-115 treatment group and placebo. The null hypothesis is that there is no difference in the mean change of DYS at Week 12 between each HMI-115 treatment group and placebo. All statistical tests will be two-sided and a significance level of 0.05 will be used unless otherwise specified. Multiplicity adjustment will not be employed with respect to the multiple dose groups in this proof-of-concept study. A test will be considered significant if the p-value is less than 0.05. Two interim analysis is planned. More details of the interim analysis are presented in Section 9.5.

The objective will also be addressed by obtaining the point and interval estimates of the mean CFB to Week 12 in the DYS NRS for each HMI-115 treatment group and placebo. In addition, hypothesis test for a statistically significant trend (upward slope) across HMI-115 doses will be performed using the 0.05 significance level.

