- Percentages will be presented to one decimal place. Percentages will not be presented for zero counts. Percentages will be calculated using n as the denominator unless otherwise specified. If sample sizes are small (n<10), the data displays will show the percentages, but any textual report will describe frequencies only.
- For quantitative measurements, change from baseline (CFB) at a particular visit will be calculated as (value at visit – baseline value).

Changes from baseline in categorical data will be summarized using shift tables where appropriate.

- P-values greater than or equal to 0.001, in general, will be presented to three decimal places after rounding. P-values less than 0.001 will be presented as "<0.001" and p-values greater than 0.999 will be presented as ">0.999".
- Confidence intervals (CIs) will be presented to one more decimal place than the point estimate.

- All values below or above a limit of quantification (e.g. <0.1 or >100) will be displayed as such in data listing. When include in table or figure summary, value may be substituted by specific value as described in corresponding section.
- For some safety parameters, the within-group and between-group differences are analyzed, but nominal p-values are provided for information only. No formal conclusion will be made based on p-values.
- For subjects who prematurely discontinued during the treatment period, their data collected during the Follow-up Period will be included in the analysis.

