The threshold for reduction in pain will be determined based on a ROC analysis using the PGIC assessment at Week 13 as an anchor and mean change of DYS measured by NRS from Baseline to Week 12 as the independent variable. The PGIC is a 7-point response scale: "Since I started taking the IMP, my endometriosis related pain has: very much improved (1), much improved (2), minimally improved (3), not changed (4), minimally worse (5), much worse (6), very much worse (7)." **The responses of "very much improved (1)" and "much improved (2)" on PGIC will be used to define PGIC responders**, and the threshold for response will be chosen to balance sensitivity and specificity. The threshold with maximum Youden's index (Youden's index=sensitivity + specificity – 1) will be selected as optimal threshold. Treatment group will be considered in ROC analysis. No other covariates will be included in the ROC analysis.

Empirical Cumulative Distribution Function (eCDF) Curve

In addition to the anchor-based method, the eCDF method will be used to determine the clinically meaningful improvement. The eCDF curves display a continuous view of the mean score change (both positive and negative) in DYS at Week 12 on the horizontal axis, with the vertical axis representing the cumulative proportion of patients experiencing up to that level of score change. An eCDF curve should be plotted for each distinct anchor category and treatment group.

Dose-Response Relationship

To study the dose-response relationship, the mean CFB to Week 12 measurement will be plotted versus nominal and log-transformed dosage (placebo, HMI-115 60mg, 120mg and 240mg). The dosage (0, 60, 120, 240) will be log-transformed using the function $\log(\text{dosage}+1)$, where \log represents the natural logarithm function. A simple linear regression model will be fitted as a function of dose to characterize the dose-response relationship. In case of lack-of-fit

of the simple linear regression model, multivariate or non-linear regression models may be explored.

The following SAS code will be used:

```
PROC REG data=data;
```

```
  MODEL cfb = log_dose / clb;
```

```
RUN;
```

```
PROC REG data=data;
```

```
  MODEL cfb = dose / clb;
```

```
RUN;
```

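### The protocol names the wrong direction for the dose trend, and neither planned dose-response slope shows that the active doses differ

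*SAP*

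**What the plan says.** Protocol 9.1 (Statistical Hypotheses) makes all tests two-sided at 0.05 unless otherwise specified. It then adds a "hypothesis test for a statistically significant trend (upward slope) across HMI-115 doses will be performed using the 0.05 significance level". SAP 2.1 fixes the sign of the outcome: "change from baseline (CFB) at a particular visit will be calculated as (value at visit – baseline value"). SAP 7.2.1 states that higher NRS scores are worse.

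SAP 7.2.5 (Dose-Response Relationship) has the mean change at Week 12 "plotted versus nominal and log-transformed dosage (placebo, HMI-115 60mg, 120mg and 240mg"). On the log axis, "The dosage (0, 60, 120, 240) will be log-transformed using the function" natural log of dosage + 1. Two simple regressions are coded: "MODEL cfb = log_dose / clb" and "MODEL cfb = dose / clb". If the linear model does not fit, "multivariate or non-linear regression models may be explored". The SAP does not repeat the word for an upward direction and names no separate trend test.

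Protocol 2.1 (Study Rationale) gives one purpose of studying several doses with placebo as to "determine appropriate dose for future pivotal studies".

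**The concern.** There are two separate problems.

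**Direction.** The protocol names a direction for the trend that, on the planned outcome scale, means less relief or more pain at higher dose. A two-sided test is unaffected. A named direction next to a rule that allows exceptions, however, leaves room for a one-sided reading, and the SAP does not settle it.

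**Interpretation.** Both regressions include the placebo arm. A slope fitted through placebo and three active doses can be significant only because active treatment differs from placebo. On the ln(dose+1) scale this is nearly all the slope measures, because adding 1 mg puts placebo far from the other three points. A significant slope could then be reported as a dose-response when the active doses are the same, or even when the lowest is best. The study is partly meant to inform dose choice, and I found no planned efficacy estimate that compares the active doses with one another.

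**Working it through.** **Inputs.** Doses 0, 60, 120, 240 mg and the ln(dose+1) score (SAP 7.2.5). 34 evaluable per arm, SD 2.0, difference 1.4, two-sided 0.05 (protocol 9.2). Assumed here: equal arms, and effect profiles with a largest effect of 1.4 points.

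**The plan's own figure.** For one dose versus placebo, 1.4 / (2.0 × √(2/34)) = 2.89. The non-central t with 66 df gives 81.2% power, which agrees with the stated 80%.

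**Direction.** An effect linear in dose gives mean differences from placebo of -0.35, -0.70 and -1.4, so the slope is -1.4/240 = -0.0058 points per mg. It is negative. A one-sided 0.05 test for a positive slope had power of at most about 0.5% under every beneficial profile tried. The two-sided test has 85% power on untransformed dose for this linear profile.

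**What the log score measures.** The scores are 0, 4.111, 4.796, 5.485. Placebo to 60 mg takes 4.111/5.485 = 75% of the axis. Deviations from the mean are -3.598, 0.513, 1.198, 1.887, with sum of squares 18.203; placebo supplies 12.945/18.203 = 71% of it. The correlation with the active-versus-placebo indicator (sum of squares 0.75, cross-product 3.598) is 3.598/√(18.203 × 0.75) = 0.974, or 95% shared variance. For untransformed dose (deviations -105, -45, 15, 135; sum of squares 31,500; cross-product 105) it is 105/√(31,500 × 0.75) = 0.683, or 47%.

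**How often each slope is significant.** Slope = Σ(deviation × effect)/SS and SE = 2.0/√(34 × SS). SE is 0.0804 for log dose and 0.001933 for untransformed dose. Power is from the non-central t with 134 df.

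- *Equal doses (-1.4 each), log:* -1.4 × 3.598/18.203 = -0.2767; ratio to SE -3.44; significant in 93%.
- *Equal doses, untransformed:* -1.4 × 105/31,500 = -0.00467; ratio -2.41; significant in 67%, or 65% by simulation, where misfit enlarges the residual.
- *Declining benefit (-1.4, -1.2, -1.0), log:* (-0.718 - 1.438 - 1.887)/18.203 = -0.2221; ratio -2.76; significant in 78%, with the sign of greater relief at higher dose.
- *Declining benefit, untransformed:* (63 - 18 - 135)/31,500 = -0.00286; ratio -1.48; significant in about 31% (29% by simulation), also with the wrong sign.

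**Would the lack-of-fit clause catch it?** A standard lack-of-fit F test at 0.05 on the log model detects misfit in about 10% of trials with equal doses and 24% with the declining profile. The SAP names no test, threshold or candidate model.

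**Active doses only.** On untransformed dose the deviations are -80, -20, 100, with sum of squares 16,800, so SE = 2.0/√(34 × 16,800) = 0.002646. With 100 df:

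- *Equal doses:* slope 0, significant in 5%, as it should be.
- *Effect linear in dose:* -0.005833/0.002646 = -2.20, power 59% (57% on log dose).
- *Emax profile (ED50 60 mg, 1.4 points at 240 mg):* power about 18%.
- *Precision:* for the 60-to-240 mg contrast, the 95% CI half-width is 180 × 0.002646 × 1.984 = 0.94 points.

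**The case against.** The strongest reply is that the log slope is only one part of the section. SAP 7.2.5 also regresses on and plots untransformed dose, and allows other models. The two regressions complement each other: the log model has 93% power for a plateau and the untransformed model 85% for a linear effect. ANCOVA gives each dose against placebo with a 95% CI, and trough concentration is plotted against pain. No passage ties dose selection to the log slope. All this stands.

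A reader might therefore go too far in three ways.

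- *That the analysis cannot guide dose choice.* The documents do not support this: the dose-by-dose comparisons, both plots and the exposure analysis all carry information.
- *That the trend test would miss benefit or count worsening as success.* That needs the parenthesis in protocol 9.1 to override the two-sided rule, which SAP 7.1 repeats.
- *That the offset of 1 mg must be replaced.* It is arbitrary and depends on the unit, but the SAP fixes the unit. An offset of 60 mg would still give a significant slope in about 83% of trials with equal doses. Any slope through placebo shares the weakness, so the choice of offset is a debatable trade-off.

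The reply does not close the main gap. The untransformed slope is also significant in about two-thirds of trials when the doses are equal, the ANCOVA contrasts are against placebo only, and the lack-of-fit clause is optional. The analysis is exploratory, in a proof-of-concept trial, which limits the weight of the point.

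**Conclusion.** The point holds in two limited parts. First, the direction in protocol 9.1 is the wrong sign for change from baseline as the SAP defines it. The consequence is small under the two-sided rule and severe only under a one-sided reading. Second, neither planned slope supports a statement that the active doses differ: equal doses give a significant slope in about 93% (log) and 65-67% (untransformed) of trials, and the log slope points the wrong way in about 78% when benefit declines modestly with dose.

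These figures assume 34 per arm, SD 2.0, equal arms and illustrative profiles; counts by arm in the SAP's primary analysis set are not given. The SAP cites protocol version 6.1 and the protocol reviewed is 6.0, so the wording of 9.1 should be checked in 6.1. The change is worth making because it is cheap and serves a stated aim of the study.

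**What to change.** 1. In protocol 9.1, describe the trend as a downward slope in change from baseline (greater reduction at higher dose), and keep the test two-sided at 0.05. Repeat the direction in SAP 7.2.5.
2. In SAP 7.2.5, keep both planned regressions and plots. Add a slope with 95% CI over the 60, 120 and 240 mg arms only, on one dose scale fixed in advance.
3. State in SAP 7.2.5 that the slopes including placebo describe the overall relationship, and that only the active-dose slope supports a statement about differences between doses.

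The cost is a wording change, one sentence and a few lines of SAS. The downside is imprecision: about 57-59% power if the effect is linear up to 1.4 points, less for a curve that flattens, and a half-width near 0.9 points for 60 versus 240 mg. A non-significant active-dose slope must not be read as evidence that the doses are equivalent.

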The use of rescue medication will be taken into account in the analysis of the primary endpoints. In the ANCOVA analysis, if a subject has at least 15% increase of rescue medication use (in terms of medication counts) compared to baseline in the EOT menstrual cycle, the measurement for Week 12 will be imputed with the baseline NRS measurement (i.e. assuming no improvement from baseline). In the MMRM analysis, if a subject has at least 15% increase of rescue medication use at a particular visit compared to baseline, the measurement at that visit will be imputed with the baseline NRS measurement. Such subjects will also be considered non-responders in the PGIC responder analysis for that visit. The visit window for the MMRM analysis will be defined in the SAP.

In addition to rescue medications, all analgesic medications taken to treat pain other than endometriosis-associated pain will be captured as concomitant medications. The pain intensity NRS measurement for endometriosis-associated pain in the days when these concomitant pain medications are used will be considered unevaluable and will be imputed by the corresponding average baseline measurement (i.e. assuming no improvement from baseline on those days).

To study the dose-response relationship, the CFB to Week 12 will be plotted versus dose. A simple linear regression model will be fitted as a function of dose to characterize the dose-response relationship. In case of lack-of-fit of the simple linear regression model, multivariate or non-linear regression models may be explored.

Version 6.0 65 of 138 April 11, 2024

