3.3 Analysis Sets

For purposes of analysis, the following analysis sets will be used:

Analysis Set	Description
Enrolled Analysis Set (ES)	All subjects who signed the ICF (including screening failures).
Full Analysis Set (FAS)	All randomized subjects who take at least one dose of IMP. For the FAS, subjects are assigned to a treatment group based on the randomization schedule, regardless of the treatment actually received.
Primary Analysis Set (PAS)	All subjects in the FAS who have surgical diagnosis. PAS will be the primary analysis set for all efficacy analyses.
Per Protocol Analysis Set (PPS)	A subset of the PAS who do not have protocol deviations that could significantly affect the results for the primary endpoints. Subjects' inclusion/exclusion from the PPS will be determined and documented prior to the database lock and unblinding. PPS will be used to demonstrate robustness of results for the primary and secondary efficacy endpoints.
Safety Analysis Set (SAF)	All subjects who received at least one dose of IMP. Subjects will be analyzed according to the IMP they actually received. SAF

	will be used for all safety analyses. In the SAP V1.3 special version for research paper publication, the SAF will be same as the PAS.
PK Analysis Set (PKS)	All subjects in the SAF who received active treatment with at least one drug concentration value, and have no major protocol deviation that could significantly impact PK assessment.
Immunogenicity Analysis Set	The immunogenicity analysis set consists of all subjects in the SAF with at least one immunogenicity value.

All protocol deviations will be reviewed and classified regarding how they affect clinical and analysis outcomes during the BDRM. Subjects may be excluded from the PPS and PKS.

Summary of the number and percentage of subjects in each analysis set with exception of the ES by treatment group and overall, based on all randomized subjects with reasons for exclusion from each analysis set will be provided.

A by-subject listing of analysis set details will be provided on the ES. This listing will be presented by treatment group and will include center, subject identifier, inclusion/exclusion flag for each set and reason for exclusion from each set.

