7.1.2 Adjustments for Covariates

The primary efficacy analysis will be adjusted for the following covariates:

- Region (stratification variable): China, the USA and Europe
- Baseline measure of DYS measured by NRS

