VAR trt01p region baseline_dys chg_dys_w6 chg_dys_w12;
RUN;
```

Analysis Step

For each of the $25 \times 25 = 625$ resulting datasets, the **ANCOVA model** with treatment, region as the fixed effects and baseline DYS measured by NRS as covariate will be used to obtain point estimate and its standard error for mean treatment different in DYS measured by NRS at Week 12.

The following SAS code for ANCOVA will be used:

```
PROC GLM data=indata;
  BY _imputation_MAR _imputation_MNAR;
  CLASS trt01p region;
  MODEL cfb = trt01p region baseline;
  LSMEANS trt01p /cl;
run;
```

Combining Step

As a final step, SAS Proc MIANALYZE is used for combining the $m=625$ point estimates and associated standard errors (from the analysis step above) are combined in order to provide a single point estimate and confidence interval for final statistical inference on the null hypotheses.

A descriptive summary of the average DYS measured by NRS as well as change from baseline by treatment group and visit (measurements of Baseline, Week 6, Week 12, and Week 24) will be presented. The Week 24 measurement is defined in the section 7.3.1.

A by-subject listing of DYS measured by NRS will be provided.

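### The dose-response slope in SAP 7.2.5 omits baseline DYS and region, and loses precision if they explain more than about 2% of the variance of the Week 12 change

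*SAP*

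**What the plan says.** Protocol 9.4.4 states the dose-response plan in one sentence: "A simple linear regression model will be fitted as a function of dose to characterize the dose-response relationship". SAP 7.2.5 repeats it and gives code for two PROC REG fits, "MODEL cfb = log_dose / clb" and "MODEL cfb = dose / clb". Dose is 0, 60, 120 or 240 mg, and log dose is log(dose+1). Neither model has another term. More complex models are optional, apply only on lack of fit, and name no covariates. The code has no by-imputation step, and the text does not say whether observed or imputed changes are used.

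The same outcome is handled differently in the primary analysis. SAP 7.1.2 says "The primary efficacy analysis will be adjusted for the following covariates" and lists region and baseline DYS. The ANCOVA in SAP 7.2.2 is fitted "with treatment, region as the fixed effects and baseline DYS measured by NRS as covariate will be used", on 625 imputed datasets pooled with PROC MIANALYZE. SAP 7.1.1 also says that the model estimating treatment effects on the primary variable will include region as a main effect.

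**The concern.** Protocol 2.1 gives, as one purpose of the trial, to "determine appropriate dose for future pivotal studies". The slope is the efficacy analysis that uses all four arms in a single estimate. The pairwise comparisons with placebo have baseline and region adjustment; the slope does not, although both variables are already collected.

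The outcome is a change from baseline, which is usually correlated with the baseline value. Where that holds, leaving baseline out puts explainable variance into the residual. The slope's confidence interval is then wider, and its power lower, than the same data allow. At stake is precision. Randomisation keeps the unadjusted slope unbiased.

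**Working it through.** **Inputs.** SD of the change 2.0, between-group effect 1.4 points, two-sided 0.05 (protocol 9.1, 9.2). 34 evaluable per arm (protocol 9.2, SAP 1.4). Doses 0, 60, 120, 240 mg. Baseline uses 1 df and region (three levels) 2 df. Assumed, because the documents do not give them: an effect linear in dose reaching 1.4 points at 240 mg, and R2, the share of variance of the change explained by the covariates.

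**The plan's own figures.** With n = 34 per arm, the noncentral t gives 80.8% power for a 1-point within-group change and 81.2% for a 1.4-point difference between two arms. Both agree with the stated 80%.

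**Unadjusted slope.** Mean dose is 105 mg. Sum of squared deviations per subject set = 105² + 45² + 15² + 135² = 31,500. SE of the fitted 240 mg versus 0 difference = 240 × 2.0 / √(34 × 31,500) = 0.464. With 134 df, power for 1.4 points is 85.0%.

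**Adjusted slope.** SE = 0.464 × √(1 − R2) / √(1 − 3/(N − 1)), with N = 4n and df = N − 5. The second factor allows for chance imbalance of three covariate terms across doses.

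| Per arm | Unadjusted | R2 = 0 | 10% | 20% | 30% |
|---|---|---|---|---|---|
| 34 | 85.0% | 84.2% | 87.8% | 91.2% | 94.3% |
| 26 (assumed) | 74.4% | 73.1% | 77.5% | 82.1% | 86.8% |

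For n = 26 the leading SE is 240 × 2.0 / √(26 × 31,500) = 0.530. That row is shown because SAP 3.3 says "PAS will be the primary analysis set for all efficacy analyses" and the PAS is limited to surgically diagnosed subjects, so it may be smaller than planned.

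**Break-even.** The two SEs are equal when R2 = 3/(N − 1): 3/135 = 2.2% at 34 per arm and 3/103 = 2.9% at 26.

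**How large R2 might be.** Let rho be the correlation of baseline with Week 12, and k the ratio of baseline SD to Week 12 SD. Baseline alone then explains (rho − k)² / (1 + k² − 2 rho k).
- k = 1: this reduces to (1 − rho)/2, so 30%, 20% and 10% at rho = 0.4, 0.6 and 0.8.
- k = 0.7, an assumed effect of the entry requirement for an NRS score of at least 4 (protocol 5.1, criterion 4): 9.7%, 1.5% and 2.7% at the same rho, and 0 at rho = 0.7.

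**Effect of the rescue rule.** SAP 7.2.2 sets an improvement (CFB below 0) to zero for rescue non-responders. A simulation with 20% non-responders at random, SD 2 and k = 1 (all assumed) lowers R2 from 30/20/10% to about 21/14/7% if the mean change is −2, and to about 24/16/8% if it is −1. At R2 of 7%, 14% and 21%, the formula above gives power of 86.7%, 89.2% and 91.5% at 34 per arm.

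**The case against.** The strongest reply is that this is a preference. The regression sits under Other Analyses, its purpose is to describe dose-response, the SAP follows the protocol, and the pairwise comparisons that carry the inference are already adjusted. The study is a proof of concept, and protocol 9.2 says its size is not based on power against placebo. All of that stands and sets the grade of the point.

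A second reply is that the gain is unknown. That also stands: no document gives R2, and the zeroing rule and a restricted baseline both push it down. What survives is the asymmetry: about one point lost if the covariates are useless, several gained if they matter moderately.

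A reader might infer that these fits are the test in protocol 9.1, "hypothesis test for a statistically significant trend (upward slope) across HMI-115 doses will be performed using the 0.05 significance level", and that coding two of them inflates the false-positive rate. The documents do not support that. Neither document labels a 7.2.5 fit as the 9.1 test, and the SAP cites protocol 6.1, which was not available. The 9.1 wording could also mean the three active doses only. Under the same assumptions, power is then 58.8% unadjusted and 62.0%, 67.1% or 72.9% adjusted, so the direction holds but not the level. No passage says that a trend will be claimed if either fit is significant, and protocol 9.4.4 specifies dose as the regressor.

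**Conclusion.** The point holds as a conditional, optional improvement. Both documents fit the slope without covariates that the primary model of the same outcome already uses. The slope is less precise than it could be if R2 exceeds about 2% (about 3% at 26 per arm). Under the assumed linear 1.4-point effect with 34 per arm, the gain is roughly 3, 6 or 9 percentage points of power at R2 of 10%, 20% or 30%, and less once the rescue rule is applied. At R2 = 0 the loss is 0.8 points, or 1.3 at 26 per arm. These figures hold the SD at 2.0 and ignore the extra variance from multiple imputation.

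It would go too far to call the unadjusted slope biased or invalid, to call it a departure from the protocol, or to treat the gain as certain.

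**What to change.** In SAP 7.2.5, fit cfb = dose + baseline DYS + region, with dose continuous and region a class variable. Fit it on the same imputed datasets as the primary analysis and pool the slope with PROC MIANALYZE. This also settles whether observed or imputed changes are used. Keep the log-dose fit, with the same covariates, as supportive, because protocol 9.4.4 specifies dose. Record the change from the simple regression in SAP section 10.

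The cost is three degrees of freedom and a little new code. PROC REG has no CLASS statement, so PROC GLM is the natural choice. The primary GLM code cannot be reused unchanged, because it enters treatment as a class factor and requests least-squares means rather than a slope. No new data are needed. The statistical downside is the small power loss given above if the covariates explain nothing.
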